5.1. Sample size calculation

A sample size calculation was performed using the method described by Cohen (1992). There is no precedent for this type of trial in this setting, so it is not known whether exposure to the Home Goals intervention may be associated with small, moderate or large effects on measures of depression, anxiety and physical activity. We have therefore followed conventional sample size calculation methods described by Cohen (1992), expecting a moderate effect size as a conservative assumption. In order to detect a moderate effect size using between-groups ANOVA, with 80% power, and an alpha level of 0.05, we estimate that at least 67 participants are needed per group. This would yield a sample size of 134. Expecting a 30% dropout rate, which is common in studies of psychological interventions, we would need to inflate the recruitment target to 192. If we recruit more than the 192, we will accept the young people onto the trial, but we will not collect or analyse their data.

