Interventions	A 6-week, psychoeducation and physical education course consisting of online live psychoeducation sessions and physical activity sessions	
Randomization and data collection	Consenting participants will be randomly assigned to two groups; 1 and 2. Participants in both groups will be asked to complete outcome measures at an initial baseline assessment, after which only participants in group 1 will access a 6-week intervention (controlled phase). Next, group 2 will access the intervention during a 6-week period (full implementation phase). Finally, we will collect further outcome measures 6 months after both groups have completed the intervention (follow-up phase).	
Planned Sample Size	Minimum recruitment target of 192 participants, expecting 30% attrition.	
Data analysis method	 Trial data will be summarised using a CONSORT diagram and analyses will be based on intention-to-treat principles. The primary analysis will compare between and within-group differences in PHQ-A at baseline and 6 weeks, using ANOVA. Secondary analyses: between and within-group analyses will be conducted for GAD-7 and the physical activity measure at baseline and 6 weeks using ANOVA. Between-group and within-group effect sizes will be calculated using Cohen's d. Completion / dropout rates will be compared between groups using chi-square analysis. 	
Study Period	18 months (12 months active study period, plus 6 months analyses and dissemination)	

2. Background and rationale

Mental health problems cause huge public health burden in adolescents globally, as evidenced by a 20% prevalence (Belfer, 2008; World Health Organization (WHO), 2005). In the UK, the demand for Child and Adolescent Mental Health Services (CAMHS) services is at an all-time high and recent research shows children and young people referrals have increased by 26% in five years (Crenna-Jennigs & Hutchinson, 2018). Furthermore, 50% of children and young people that are assessed, wait more than 18 weeks to start treatment and over 3% wait over 12 months (Crenna-Jennings & Hutchinson, 2018).

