3.3. Hypotheses

- A) Exposure to the intervention will be associated with significantly lower mean score of depression and anxiety by comparison to a waitlist (delayed intervention) control group
- **B)** After the control group is exposed to the intervention, there will be no significant differences in mean depression and anxiety level between the two groups (immediate intervention group, delayed intervention group)
- C) Mean depression and anxiety severity for all participants at the end of the 6-month follow-up period will be significantly lower than baseline severity (prior to intervention), but not significantly different to end-of-treatment severity, indicating maintenance of gains
- **D)** Attitude towards physical exercise will significantly improve following the intervention, and be maintained at the 6-month follow-up period.

4. Study design

This will be a pragmatic, stepped wedge, open-label, randomised controlled trial. Consenting participants will be randomly assigned to two groups, by a research assistant using a computerized randomization algorithm (applying a simple 1:1 randomization schedule). Participants will take part in one of the two 6-week interventions, depending on their group assignment. They will complete an online survey with standardised measures at baseline (prior to starting the interventions), after 6 weeks (after group 1 has finished and prior to group 2 commencing), after 12 weeks (post-treatment) and finally after 6 months (follow-up). All measures will be completed online using an industry-standard survey system which automatically sends email reminders to consenting participants.

The interventions will be delivered using an online approach; weekly online video-conference sessions involving half an hour of psychoeducation and half an hour of physical activity. Both interventions will involve a total of six 1-hour sessions delivered once per week using video-conferencing software that can involve large groups of participants. The study will be carried out in four phases, which are illustrated in Figure 1.

[figure not shown]

Figure 1. Trial design and measurement time-points

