5.2. Primary analysis

Trial data will be summarised using a CONSORT diagram and all analyses will be based on *intention-to-treat* principles. Missing data will be imputed using an expectation-maximization algorithm (Schafer & Olsden, 1998), prior to conducting formal analyses.

The primary hypothesis test (A) will be based on comparing mean outcome measures between groups at week 8, as shown in Figure 1. Mean PHQ-A scores will be compared between groups using analysis of covariance (ANCOVA), controlling for baseline severity.

Sensitivity analyses will be performed to assess the robustness of the main findings. This will involve repeating the above analysis including a random intercept for each trial site and additionally introducing "role" as a covariate (admin; mental health; other clinical role) and any other baseline demographics that may be unbalanced between groups.

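### Recruits beyond 192 join the trial but are neither measured nor analysed, which as written excludes randomised participants by rule

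*Protocol*

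**What the plan says.** Protocol Section 5.1 derives a recruitment target of 192 and then sets a rule for any excess: "we will accept the young people onto the trial, but we will not collect or analyse their data".

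Other parts of the protocol bear on the same people:

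- **Synopsis, Planned Sample Size:** "Minimum recruitment target of 192 participants, expecting 30% attrition".
- **Section 4, Study design:** the trial is open-label, and consenting participants are assigned at random, "applying a simple 1:1 randomization schedule". No upper limit is given.
- **Section 4.4, recruitment process:** consenting participants are allocated at random within their region and told their group by email within a week of consenting. No exception is made after number 192.
- **Section 4.4, data collection:** the baseline measures are to be completed by all participants, followed by a shorter survey at each later time-point.
- **Section 5.2:** "Trial data will be summarised using a CONSORT diagram and all analyses will be based on" intention-to-treat principles.

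**The concern.** Section 5.1 states a rule, so this is not a detail left for a later analysis plan. It places the extra young people on the trial. Under Sections 4 and 4.4, anyone who consents to the trial is randomised and measured. Under Section 5.2, anyone randomised belongs in the analysis. Section 5.1 says that they are not measured and not analysed. These statements cannot all be followed once recruitment passes 192.

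Two things are at stake. The first is the definition of the analysed set: nothing says whether the 192 are the first to consent, the first randomised or the first to complete baseline. The second is precision: information from randomised participants who receive the sessions anyway is never gathered, and outcomes missed at their time-points cannot be recovered later.

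There is also a practical consequence. Extra participants in group 2 would wait six weeks for a comparison that ignores them. Without surveys, they could not meet the survey-completion condition for either prize draw in Section 4.4.

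**Working it through.** **1. The plan's own figure.** Section 5.1 states that "at least 67 participants are needed per group", hence 2 × 67 = 134, and then "Expecting a 30% dropout rate". Inflating, 134 / (1 − 0.30) = 191.4, which rounds up to 192. The target reproduces.

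The 67 rests on "expecting a moderate effect size as a conservative assumption", "with 80% power, and an alpha level of 0.05". No numerical effect size or sidedness is given. Assuming d = 0.5 and a two-sided test, a t-test or two-group ANOVA needs 64 per group, and 67 gives about 82% power. The difference is on the safe side and does not affect this point. The 30% attrition is already inside the 192.

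**2. Where the statements meet.** Take the 193rd young person to consent.

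| Place | What happens to this person |
|---|---|
| Synopsis | Within a target described as a minimum |
| Sections 4 and 4.4 | Randomised 1:1 and told the group by email |
| Section 4.4, data collection | Measured, as are all participants |
| Section 5.2 | Analysed, under intention-to-treat |
| Section 5.1 | On the trial, but not measured and not analysed |

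Section 5.1 conflicts with the rows on measurement and analysis. It also turns the synopsis's minimum into a ceiling on data.

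**3. When the choice of the 192 could matter.**

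- *Counted by order of consent, before allocation.* Membership cannot depend on arm or outcome. With simple 1:1 randomisation the first 192 are an unbiased comparison, and only precision is lost.
- *Counted after the allocation email, for example at baseline completion.* The synopsis describes random assignment first and the baseline assessment after it. Participants know their group by then, so who gets counted could differ by arm.

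The protocol does not say which applies.

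**4. Precision lost.** Let R be the number recruited. With the same attrition and variance throughout, the evaluable number is 0.7R, the 0.7 cancels, and the standard error using only 192 relative to using everyone is √(R/192). The documents give no recruitment forecast, so the values of R are assumptions.

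| R (assumed) | Discarded | Share discarded | √(R/192) |
|---|---|---|---|
| 192 | 0 | 0% | 1.00 |
| 230 | 38 | 38/230 = 16.5% | 1.09 |
| 250 | 58 | 58/250 = 23.2% | 1.14 |

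**5. The same in power.** With a two-sided 5% t-test, 1:1 allocation and 30% dropout, analysing everyone would give:

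| Assumed d | R = 192 | R = 240 |
|---|---|---|
| 0.5 | 82% | 90% |
| 0.4 | 63% | 73% |
| 0.3 | 41% | 49% |

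Section 5.1 allows that the effect may be small, so the lower rows are relevant.

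**The case against.** The best defence is that Section 5.1 singles these young people out for different handling and never says that they are randomised. It could mean that late applicants receive the course as a service, outside the evaluated sample, in which case intention-to-treat holds for the 192. That reading is possible, but the sentence puts them on the trial, and Sections 4 and 4.4 make no exception. The text needs to say it.

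A recruitment floor and a limit on data can also coexist in principle. That softens the conflict with the synopsis but does not touch the conflict with Sections 4.4 and 5.2.

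Several stronger conclusions that a reader might infer are not supported:

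- *That the rule biases the comparison or unbalances the arms.* This would need the 192 to be settled after allocation. The most natural meaning of recruiting more than 192 is order of recruitment, which is harmless in this respect. The protocol leaves the risk open but does not create it outright.
- *That a CONSORT diagram could not accommodate the exclusions.* It can show them with the reason. It could not describe the result as an intention-to-treat analysis of everyone randomised.
- *That the expected 30% loss makes the limit worse.* The 192 already allows for it.
- *That nothing is saved.* The documents give no costs. Surveys are online with automatic reminders (Section 4), but the team also keeps email and pseudonym records, and each extra participant adds up to four rounds of mental-health data on a young person. The saving is probably small, not nil.

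**Conclusion.** The point holds as an internal contradiction with a contingent cost. As written, Section 5.1 leaves randomised participants out of measurement and analysis by rule, against Sections 4, 4.4 and 5.2, and treats as a data ceiling what the synopsis calls a minimum.

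The size depends on recruitment. At or below 192 nothing is lost. At assumed totals of 230 or 250, the standard error is about 9% or 14% larger than it need be. This forgoes precision above plan: the trial is not underpowered by the rule, since 192 recruits still give about 82% power at an assumed d of 0.5.

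Whether validity is also at risk turns on how the 192 are identified. Fixing them by order of consent before allocation removes that risk. The sentence should be changed before recruitment closes.

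**What to change.** Replace the sentence in Section 5.1 with: *All randomised participants will be surveyed and included in the intention-to-treat analysis; 192 is the minimum target.* This agrees with the synopsis and with Sections 4, 4.4 and 5.2 as they stand.

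If a firm limit is wanted, state that consent and randomisation close at 192 by order of consent, and that any further places are offered outside the trial without randomisation. Show those later applicants in the CONSORT diagram as not randomised, and reconcile the synopsis, the allocation and data-collection text in Section 4.4, and Sections 5.1 and 5.2 with that limit.

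The first option costs one sentence plus survey administration and data handling for the extra participants, who would receive the sessions in any case. The second costs a few lines of text and a rule for closing the consent link.

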5.2. Primary analysis

Trial data will be summarised using a CONSORT diagram and all analyses will be based on *intention-to-treat* principles. Missing data will be imputed using an expectation-maximization algorithm (Schafer & Olsden, 1998), prior to conducting formal analyses.

The primary hypothesis test (A) will be based on comparing mean outcome measures between groups at week 8, as shown in Figure 1. Mean PHQ-A scores will be compared between groups using analysis of covariance (ANCOVA), controlling for baseline severity.

Sensitivity analyses will be performed to assess the robustness of the main findings. This will involve repeating the above analysis including a random intercept for each trial site and additionally introducing "role" as a covariate (admin; mental health; other clinical role) and any other baseline demographics that may be unbalanced between groups.

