- The first prize draw will take place at the end of the 6-week intervention phase for each group (week 12 in Figure 1). To be eligible for inclusion in this prize draw, participants should have attended at least four intervention sessions and have completed the three online surveys up to that point. The prize will be a £20 Amazon voucher, and there will be one prize per participating site (trial site).
- The second prize draw will take place at the end of the 6-month observational phase (week 36 in Figure 1). To be eligible for inclusion in this prize draw, participants should have attended at least four intervention sessions and have completed all four online surveys. The prize will be a £50 Amazon voucher, and there will be one prize per participating site (trial site).
- In accordance with the University of Sheffield's policy for the ethical use of incentives in research, the prize winners will receive their electronic voucher code via email and they will be asked to return a signed receipt via email, which includes their name and work address, which is essential for auditing purposes and for legal reasons.

5. Statistical analysis plan

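### Section 5.2 fills in missing outcomes by EM and then runs ANCOVA as if they were observed, so the standard error is too small or, if arm is left out of the EM model, the effect is diluted

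*Protocol*

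**What the plan says.** Protocol section 5.2 gives the missing-data method in one sentence: "Missing data will be imputed using an expectation-maximization algorithm", with a methods citation, and the step is done "prior to conducting formal analyses". The same section says that "all analyses will be based on *intention-to-treat* principles". The primary test follows: "Mean PHQ-A scores will be compared between groups using analysis of covariance (ANCOVA), controlling for baseline severity".

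The section does not mention more than one completed dataset, a pooling rule or a variance correction. It does not say whether treatment arm enters the EM model, or whether filled values are conditional means or random draws. Its sensitivity analyses vary trial site and covariates, not the handling of missing data.

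Section 5.1 says how much loss is planned for. It first states that "we estimate that at least 67 participants are needed per group", 134 in total. It continues: "Expecting a 30% dropout rate, which is common in studies of psychological interventions", and concludes that "we would need to inflate the recruitment target to 192".

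**The concern.** An EM algorithm is a sound way to estimate means and covariances from incomplete data. Using it to write values into the empty cells, and then passing the file to a complete-data ANCOVA, is a different matter. The ANCOVA cannot tell a filled value from a measured one, so it uses the full sample size and degrees of freedom and ignores the uncertainty about the missing values.

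The two sections also pull against each other. Section 5.1 treats 30% of participants as contributing no information and raises recruitment to make up for them. Section 5.2 then counts those participants as if they did contribute.

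At stake are the confidence interval and p-value of the primary PHQ-A comparison or, under a different EM model, the size of the estimated effect. Imputation precedes all formal analyses, so the secondary ANCOVAs and paired comparisons in section 5.3 would use the same filled data. That knock-on effect was not sized.

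**Working it through.** **Inputs from the protocol.** 67 per group, 30% dropout, target 192 and alpha 0.05 (section 5.1); 1:1 allocation (section 4), so 96 per arm.

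**Assumed inputs.** Two-sided test; a moderate effect taken as 0.50 SD; baseline-outcome correlation 0.3, 0.5 or 0.7; normal outcomes; equal loss in both arms.

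**The plan's own figure.** 134 / (1 − 0.30) = 191.4, rounded up to 192, which agrees. At 30% loss, 192 − 134 = 58 outcomes would be filled in.

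**Closed form, conditional-mean fill with arm in the model.** The filled points lie exactly on the fitted ANCOVA surface. The estimated effect and the residual sum of squares are therefore the same as from the 134 observed cases. Two things change in the reported standard error: the residual degrees of freedom rise from 134 − 3 = 131 to 192 − 3 = 189, and the sample size rises from 134 to 192.

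- Reported SE / true SE = √(131/189) × √(134/192) = 0.833 × 0.835 = 0.70.
- Type I error = 2 × [1 − Φ(1.96 × 0.70)] = about 17%.

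For a missing fraction m the ratio is approximately 1 − m, which gives type I error of 7.8%, 11.7% and 17.0% at m = 0.10, 0.20 and 0.30.

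**Simulation.** 96 per arm, outcomes missing completely at random, ANCOVA on the filled file as if complete, 6,000 replicates. Multiple imputation used 20 imputations with Rubin's rules and 1,500 replicates, so its type I error carries noise of about ±1.1 points.

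| Method | Missing | SE ratio | Type I error |
|---|---|---|---|
| EM mean fill, arm in model | 10% | 0.89 | 7.9% |
| EM mean fill, arm in model | 20% | 0.80 | 11.9% |
| EM mean fill, arm in model | 30% | 0.69-0.70 | 16.6-17.1% |
| One random draw, arm in model | 30% | 0.75-0.76 | 13.9-14.3% |
| EM mean fill, arm omitted | 30% | 1.00 | 4.7-5.0% |
| Multiple imputation, arm in model | 30% | 0.99-1.01 | 4.0-5.6% |
| ANCOVA on observed cases | 30% | 1.00 | 4.7-5.1% |

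The ranges in the 30% rows are across the three correlations, so the result does not depend on that assumption. The 10% and 20% rows use correlation 0.5. With outcomes missing at random given baseline instead (5,000 replicates, correlation 0.5, 30% missing), type I error was 17.5% for mean fill and 14.6% for a random draw.

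In interval terms, at correlation 0.5 and 30% missing the reported SE is 0.104 SD against a true 0.150 SD. The 95% half-width is printed as 1.96 × 0.104 = 0.20 SD when it should be 1.96 × 0.150 = 0.29 SD.

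**Arm left out of the EM model.** The filled 30% in each arm lie on one common line and carry no arm difference, so the expected estimate is (1 − 0.30) × 0.50 = 0.35 SD. The simulation gave 0.348 (0.342 with missingness depending on baseline). Power for a true 0.50 SD effect was 91% with mean fill and 78% with a random draw, against 91% for observed cases.

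**After the fix.** At a true effect of 0.50 SD and 30% missing, multiple imputation and observed-case ANCOVA both estimate 0.50 SD, each with 91% power.

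**The case against.** **The protocol never says that the imputation is single.** True. It names an algorithm and cites a source, and a separate analysis plan may give more detail, including the variables in the EM model. If pooled multiple imputation is meant, the objection falls once the text says so. But the protocol itself prescribes impute-then-analyse for its primary test, and one completed dataset is the plain reading.

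**The p-value is not wrong in every case.** This stands. A reader might infer that any EM fill invalidates the test. With arm omitted, type I error stays near 5%, and with mean fill power equals that of the observed cases. What fails there is the estimate, and with it the placing of the interval. Nor is all residual variation always lost: a random draw restores the scatter, though type I error is still about 14-15% at 30% missing.

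**Thirty per cent may be too pessimistic for the primary comparison.** This also stands. Section 5.1 attaches no time-point to the dropout, surveys run to week 36, and the primary comparison is at the first follow-up. Section 5.1 does use 30% to size the primary test, so it is the fair planning case, but not a forecast for that survey.

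**The prize draws.** Section 4.4 makes eligibility for the first draw conditional on attendance: "participants should have attended at least four intervention sessions and have completed the three online surveys up to that point". When group 1 finishes, only its low attenders can already be ruled out, because group 2 has not started. A reader might infer that this makes missingness informative in one arm. It could in principle lower their response, but the documents give no response rates with or without the rule, so neither the existence nor the size of a bias can be shown. Eligibility is also a separate design choice that neither causes nor cures the imputation problem.

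**Conclusion.** The point holds on the plain reading of section 5.2. A single EM fill followed by complete-data ANCOVA goes wrong in one of two ways, and the protocol does not say which would apply.

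- **Arm in the EM model:** the standard error is understated, and type I error is about 8% at 10% missing, 12% at 20% and 17-18% at 30% with mean fill.
- **Arm omitted:** the test keeps its nominal level, but at 30% missing the effect is diluted by about 30%.

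The sizes rest on normal outcomes, equal loss by arm and an assumed 0.50 SD effect. The understatement of the standard error does not require dropout to be related to outcome. The documents do not support saying that the primary p-value will be wrong whatever EM model is used, that 30% of primary outcomes will be missing, or that the prize draws bias the comparison by any stated amount.

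**What to change.** Replace the EM sentence in section 5.2 with one of these:

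- **Multiple imputation**, with arm and baseline scores in the imputation model or imputation done separately by arm, at least 30 imputations, and estimates and standard errors combined by Rubin's rules.
- **Analysis of observed data**, either by a likelihood-based mixed model or by baseline-adjusted ANCOVA on participants with an observed outcome.

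If pooled multiple imputation was intended all along, saying so, with the number of imputations and the role of arm, is enough.

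The cost is a sentence of protocol text, a little more programming and wider, honest confidence intervals. Recruitment need not change, because section 5.1 already inflates the target so that 134 observed outcomes suffice. Prize-draw eligibility need not change for this point.

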5.3. Secondary analyses

ANCOVA (and sensitivity analyses) described above will be repeated at each of the time-points illustrated in Figure 1 (weeks 0, 6, 12, 36), using the PHQ-A, and using the GAD-A as an outcome, controlling for baseline scores. Outcomes at 6-months follow-up (pooled for both groups) will be compared to outcomes at the baseline assessment, using paired-samples t-tests (or an appropriate non-parametric test depending on the distribution of the data).

These analyses will be repeated at each of the post-intervention time-points illustrated in Figure 1 (weeks 6, 36), using the WEMWBS sub-domain scores. These between and within-group comparisons will also be summarised using effect sizes (Cohen's d).

Post-intervention measures (weeks 6, 36) will be compared to baseline measures (week 0) within each group, using paired-samples t-tests or an appropriate non-parametric test depending on the distribution of the data. Within-sample pre-post treatment effect sizes will also be computed using the method proposed by Minami et al. (2008).

We will carry out an exploratory analysis of knowledge and levels of activity before and after the intervention.

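### Section 5.2 sets the primary test at week 8, when nothing is measured and group 2 is already in treatment, and the synopsis names a different primary method

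*Protocol*

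**What the plan says.** Section 5.2 of the protocol fixes the time of the confirmatory comparison: "The primary hypothesis test (A) will be based on comparing mean outcome measures between groups at week 8, as shown in Figure 1". Its next sentence fixes the method: "Mean PHQ-A scores will be compared between groups using analysis of covariance (ANCOVA), controlling for baseline severity".

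The synopsis, under the data analysis method, gives another definition: "The primary analysis will compare between and within-group differences in PHQ-A at baseline and 6 weeks, using ANOVA".

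The measurement schedule is in section 4 (Study design). After baseline, surveys come "after 6 weeks (after group 1 has finished and prior to group 2 commencing), after 12 weeks (post-treatment) and finally after 6 months (follow-up". Section 5.3 reports the content of the figure as "time-points illustrated in Figure 1 (weeks 0, 6, 12, 36". Section 4.4 ties the second prize draw, at week 36, to having "completed all four online surveys". The synopsis describes the first phase as one in which "only participants in group 1 will access a 6-week intervention (controlled phase"; group 2 has its course in the next 6-week period. Hypothesis A in section 3.3 compares exposure to the intervention with a waitlist control.

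**The concern.** One sentence defines the time of the trial's primary test, and the time it names has no planned data. If the sentence were followed by adding a week-8 survey, the comparator would no longer be an untreated waitlist, because group 2 starts after the week-6 survey. Read literally, the only valid treated-versus-untreated comparison, PHQ-A at week 6, is a secondary analysis under section 5.3.

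The method is a separate contradiction, and correcting the week does not remove it. A baseline-adjusted ANCOVA and an ANOVA of between- and within-group differences are different models with different precision. A within-group change is also not a randomised comparison, so it does not belong in the definition of a test of hypothesis A. With two methods on record for one confirmatory test, the protocol does not settle which result is the primary one.

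**Working it through.** **1. Is week 8 a measurement point?** The relevant statements, side by side:

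| Place in the protocol | Time-points given |
|---|---|
| Section 4, Study design | baseline, 6 weeks, 12 weeks, 6 months |
| Section 4.4, prize draws | three surveys up to week 12, four in all by week 36 |
| Section 5.3 | weeks 0, 6, 12, 36 |
| Section 5.4 | weeks 0, 6 and 12 for change scores |
| Synopsis, primary analysis | baseline and 6 weeks |
| Section 5.2, primary test | week 8 |

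The set {0, 6, 12, 36} does not contain 8. Figure 1 is not reproduced in the text available, but section 5.3 states its time-points, so the check does not depend on seeing it.

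**2. Is week 8 inside the controlled phase?** The controlled phase lasts 6 weeks. The second survey is taken "after 6 weeks (after group 1 has finished and prior to group 2 commencing". Group 2's 6-week course then runs from about week 6 to week 12, and 6 < 8 < 12. Of the surveys after baseline, only week 6 compares a treated group with an untreated one.

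**3. The plan's own sample size (section 5.1).** Inputs: 67 per group, 80% power, alpha 0.05, 30% dropout. The effect is called moderate without a number; d = 0.5 and a two-sided test are assumed here. A two-sample t-test with 67 per group then has 81.9% power (64 per group would reach 80%). Dropout: 134 / 0.70 = 191.4, rounded up to 192, as stated. The sample size is therefore reproduced closely and is not part of the problem. With ANCOVA at week 6 and the same d, 67 per group gives power of about 82%, 86%, 92% and 98% at r = 0, 0.3, 0.5 and 0.7 (normal approximation).

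**4. How much does the choice of method matter?** Let r be the correlation between baseline and week-6 PHQ-A. The protocol gives no value, so a range is used. With equal variance at both times, scaled to 1, the variance behind the group comparison is:

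- ANCOVA: 1 − r²
- change-score or group-by-time ANOVA: 2(1 − r)
- ANOVA of the week-6 score alone: 1

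The sample-size ratio against ANCOVA is 2(1 − r)/(1 − r²) = 2/(1 + r) for the change-score model and 1/(1 − r²) for the week-6 score alone.

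| r (assumed) | 2/(1 + r) | 1/(1 − r²) |
|---|---|---|
| 0.3 | 2/1.3 = 1.54 | 1/0.91 = 1.10 |
| 0.5 | 2/1.5 = 1.33 | 1/0.75 = 1.33 |
| 0.7 | 2/1.7 = 1.18 | 1/0.51 = 1.96 |

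The two readings move in opposite directions as r rises. The synopsis wording suggests the first and the phrase in section 5.1 (between-groups ANOVA) could suggest the second, so no single figure can be given.

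**5. A hypothetical week-8 survey, for completeness.** By then group 2 could have had about 2 of 6 sessions. If it had gained 1/6, 1/3 or 1/2 of a 0.5 SD effect while group 1 kept all of its gain, the contrast would be 0.42, 0.33 or 0.25 SD. Unadjusted t-test power at 67 per group would be 67%, 48% or 30%. No such survey is planned, so these figures do not measure a consequence of the protocol.

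**The case against.** The best defence is that week 8 is an isolated slip. The synopsis gives 6 weeks, section 4 places the 6-week survey exactly at the end of the controlled phase, and section 5.3 already applies the same ANCOVA to PHQ-A at week 6. Only week 6 fits both hypothesis A and the schedule. The ANOVA wording sits in a short synopsis line, whereas section 5.2 is explicit.

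Most of this stands. It means that a reader should not conclude that the primary comparison is impossible to carry out: the data and the model for week 6 are both in the protocol. It does not make the contradiction harmless. The slip is in the sentence that defines the primary test, and it leaves the valid comparison classed as secondary. Section 5 also carries other text that does not fit a trial in school pupils: 5.2 names a staff-role covariate, and 5.4 names the OLBI as the target outcome. A reader therefore cannot safely decide which statements were meant. A wrong week also does not explain why two methods are named.

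Two further inferences are tempting. One is that the trial loses power from 82% to 48%. That concerns a survey nobody plans, and it rests on d = 0.5, linear benefit and an unadjusted test. The other is that ANCOVA should also replace ANOVA for physical activity, which the synopsis lists beside the GAD measure. Section 5.3 treats activity as exploratory, and section 4.3 describes only questions about activity level, with no scored scale.

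**Conclusion.** The point holds. Section 5.2 places the primary test at a time with no survey, inside group 2's treatment period, and the synopsis names a different method for the same test. Both are contradictions in what the protocol itself states, not details left to a separate analysis plan, and they rest on no numerical assumption.

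The intended time-point is recoverable as week 6, so the finding is that the rule is wrong as written, not that the trial cannot answer its question. The planned numbers suit a week-6 comparison. No loss of power follows from the week-8 wording. The difference between the methods is real, but its size is known only as a range, a sample-size ratio of 1.10 to 1.96 for r between 0.3 and 0.7, depending on which ANOVA was meant. That two definitions leave room to choose after seeing the data is a possibility; nothing in the protocol shows that it is intended.

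**What to change.** - In section 5.2, replace week 8 with: week 6 (end of the controlled phase, before group 2 starts).
- In the synopsis, define the primary PHQ-A analysis as a between-group ANCOVA of the week-6 score adjusted for the baseline score, and use the same wording for the GAD measure, to match section 5.3.
- Remove within-group differences from the definition of the primary test. They can stay as the descriptive and paired analyses of section 5.3.
- Leave physical activity as exploratory, as in section 5.3.

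The cost is protocol wording only. It needs no new survey, visit or participant and no change to the sample size. The correction should be dated before any outcome data are compared between groups.
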